4.1 Data Capture

4.1.1 Database

The primary method of data collection is via the study database, developed within the chosen Electronic Data Capture (EDC) platform, IBM Clinical Development. The database has been designed based on the final protocol, the system/core configuration, electronic Case Report Form (eCRF) specifications and/or mock eCRF and consistency check specifications.

Data will be entered directly into the EDC system. Site-collected data will be entered directly from source notes at the site and will be verified by Clinical Research Associates (CRAs) to ensure data integrity.

Refer to the Data Management Plan for further details.

4.1.2. Third Party Data

4.1.2.1 Safety Laboratory

Central safety laboratory data will be received from Sullivan Nicolaides (SNP) Pathology Central Laboratory as specified in the Data Transfer Specification. At least one transfer will be delivered prior to database lock and reconciled against CRF data. Following successful reconciliation and resolution of any data issues, the data will be incorporated into the End of Study analysis.

No unit conversion of laboratory data will be performed.

4.1.2.2 PK Laboratory

PK samples will be analysed by Swiss BioQuant Central (SBQ) and PK parameters will be derived by PharmaKinetic. Final PK assay data will be transferred to SSR, as specified in the SBQ DTS, for incorporation into the PC SDTM.

4.1.2.3 PD Laboratory

All parasitaemia data will be generated by the Queensland Paediatric Infectious Diseases (QPID) laboratory and captured electronically using MARS (18S qPCR parasitaemia data). All parasite life-stage data (i.e. gametocytemia and ring-stage parasites) will be generated by the QPID laboratory and transferred electronically to the Queensland Institute of Medical Research (QIMR) Berghofer and this data will be used for PK/PD modelling. QIMR will provide the 'raw' PCR data 18s and RT-PCR to SSR as per DTS, and final PD parameters will be in the PRR report.

4.1.2.4 PK/PD Laboratory

PK/PD analysis will be performed by MMV, Pharmacometrics. SSR will be required to provide the PK concentration and parasitemia data, as well as any CRF datasets required to perform the PK/PD analyses (e.g. demographics, drug administration data).

4.2 Statistical Programming

4.2.1 Programming Specifications

4.2.1.1 Safety Analysis

Programming specifications will be prepared to detail the SAS programming of CDISC (SDTM and ADaM) datasets and listings, tables and figures.

4.2.1.2 PD Analysis

Data manipulation and data analyses for all PD data will be performed using R (highest version available).

4.2.1.3 *PK Analysis*

The estimation of pharmacokinetic parameters by non-compartmental analysis (NCA) methods will be performed using Phoenix WinNonlin software (v8.3 or a more recent version, Certara USA, Inc., USA).

4.2.1.4 *PKPD Analysis*

All data processing, analysis, model setup and modeling result analysis including goodness-of-fit plots will be performed in R 4.1.3 and IQRtool package 1.10.0 [IQRtools]. NLME modelling will be performed with Monolix 2019R1 [MLX19] using Stochastic Approximation Expectation Maximization (SAEM) for parameter estimation.

4.2.2 *Baseline*

Baseline will be defined as:

Safety

- The last scheduled observation prior to the administration of the malaria challenge inoculum [Inoculation Baseline],
- The last scheduled observation prior to the first administration of IMP [Treatment Baseline].

PD

- The last observation prior to the administration of the IMP for PD data.

PK

- The last observation prior to the administration of the IMP for PK data.

4.2.3 *Change from Baseline*

Change from Baseline will be calculated as:

$$\text{Change from baseline} = (\text{postbaseline value}) - \text{baseline value}$$

4.2.3.1 *Days relative to Inoculation*

$$\text{Days} = (\text{Assessment Date} - \text{Inoculation Administration Date}) + 1$$

4.2.3.2 *Days relative to IMP administration*

$$\text{Days} = (\text{Assessment Date} - \text{First Study Drug Administration Date}) + 1$$

4.2.4 *IMP Treatment Groups*

Tabulations will summarise data by the following IMP groups and these may vary for each cohort:

Pyr 360 mg
Pyr 540 mg
Pyr 720 mg
Overall

5. ANALYSIS SETS

The analysis sets to be used for the analyses will be: Full Analyses set (FAS), IMP set, PK set, PD set and PK/PD set.

The number of participants in each analysis set will be summarised, with a corresponding listing.

5.1 Analysis Set Descriptions

5.1.1 *Full Analysis Set*

The Full Analysis Set (FAS) will consist of all enrolled participants, i.e. participants that received the malaria challenge agent.

5.1.2 *IMP Set*

The IMP Set will include all enrolled participants administered with the IMP.

5.1.3 *PK Analysis Set*

The PK analysis set will include all participants with at least one available valid (i.e. not flagged for exclusion) PK concentration measurement, who received any study treatment and experienced no protocol deviations with relevant impact on PK data.

5.1.4 *PD Analysis Set*

The PD analysis set will include all participants inoculated with the malaria challenge agent and who develop parasitaemia detectable by qPCR, received a dose of pyronaridine, and have no protocol deviations or other circumstances that would exclude them from the PD analysis.

5.1.5 *PK/PD Analysis Set*

The PK/PD analysis set will include all participants from the PK set and all participants from the PD set.

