10. PRIMARY ENDPOINT ANALYSIS (PK/PD ANALYSIS)

Analysis Set: PK/PD Analysis Set

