10.1 Overview of methodology for PK/ PD Modelling

A population PKPD model will be derived from the concentrations and parasitemia observed in the challenge participants. It is achieved by sequentially developing a population PK model to describe the observed individual PK profiles and a population PD model for quantifying the relationship of blood concentrations and the parasite clearance.

Then, the PD model is combined with a PK model in malaria patients to predict the parasitemia profiles this population, assuming the PKPD relationship will be the same in patients as in the challenge participants.

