10.5.1 PK modeling data set

Observations below the lower limit of quantification (LLOQ) will be censored by setting the CENS column for these observation records to 1 and setting the corresponding dependent variable (DV) column to the LLOQ (→ M3 method). Observation records with missing values and records with missing times will be ignored. Records flagged to be ignored will be removed from the dataset. Observations not analysed in the PK modelling (i.e., all parasite count records) will be removed. As a result, the PK modelling dataset only contains Pyronaridine tetraphosphate dosing records and Pyronaridine blood concentration records.

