10.5.2 PD modeling data set

Observations below the LLOQ will be censored by setting the CENS column for these observation records to 1 and the corresponding DV value to the LLOQ, i.e., 10 p/mL (→ M3 method). Total counts of parasites for which counts of gametocytes exceeded 10% of total counts are flagged to be ignored (by setting the column IGNORE to "gametocytes"). Observation records with missing values and records with missing times will be ignored. Records flagged to be ignored will be removed from the dataset. Observations not analysed in the PD modelling analysis (i.e., concentration records) will be removed. As a result, the PD modelling dataset only contains Pyronaridine tetraphosphate dosing records, total parasite counts (i.e., triplicates).

The model baseline parasitemia value is added to the dataset as geometric mean of parasite counts at time of first Pyronaridine tetraphosphate dose.

The total parasite counts will be log-transformed for the PD modelling and estimated individual PK model parameters will be added to the dataset as regressors.

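### SAP 5.1.5 defines the primary PK/PD set as the union of the PK and PD sets, so exclusion from one set alone does not keep a participant out of the PD step

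*SAP*

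**What the plan says.** SAP 5.1.3 limits the PK set to participants with at least one valid concentration "who received any study treatment and experienced no protocol deviations with relevant impact on PK data". SAP 5.1.4 limits the PD set to dosed participants with detectable parasitaemia who "have no protocol deviations or other circumstances that would exclude them from the PD analysis". Each set therefore has its own exclusion rule.

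SAP 5.1.5 then combines them: "The PK/PD analysis set will include all participants from the PK set and all participants from the PD set". The first line of SAP Section 10 names this set for the primary endpoint: "Analysis Set: PK/PD Analysis Set".

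The primary analysis runs in steps. SAP 10.1 says of the population PKPD model: "It is achieved by sequentially developing a population PK model to describe the observed individual PK profiles and a population PD model". SAP 10.6.1 lists three: a population PK model, a growth model fitted to counts taken before treatment, and a PKPD model that takes the individual PK and growth estimates as inputs. SAP 10.5.2 repeats the link to PK: "estimated individual PK model parameters will be added to the dataset as regressors".

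Protocol 9.3 leaves the definition of the PK/PD population to the SAP. Neither document says elsewhere that membership of both sets is required.

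**The concern.** The exclusions in 5.1.3 and 5.1.4 are there to keep unreliable data out of the analyses that depend on them. A union undoes this for the primary endpoint, because anyone removed from one set comes back through the other.

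Two routes matter, both at the PD step:

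- **Excluded from PK, kept through PD.** The participant's parasite counts are modelled against individual PK estimates that rest on concentrations, or a dosing record, already judged unfit for PK analysis.
- **Excluded from PD, kept through PK.** Parasite counts judged unfit for the PD analysis can still be used to estimate drug effect. As an illustration, suppose a participant takes a drug with antimalarial activity during follow-up (exclusion criterion 29 in Protocol 5.2 gives examples) and is removed from the PD set for it. The counts are neither missing nor, necessarily, taken after rescue or dominated by gametocytes. No listed rule drops them, and the model would credit that killing to pyronaridine.

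Either route could affect Emax and EC50, and from there MIC, MPC90 and the model-based PRR48 (SAP 10.7) and the patient simulations (SAP 10.8).

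**Working it through.** The plan gives no figure to reproduce: the maximum of 18 rests on experience and not on a formal calculation (Protocol 9.2). The check is a count of set sizes, followed by a reading of the dataset rules.

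**Set sizes.** Let N be the number dosed, a the number excluded from the PK set only, b from the PD set only, and c from both.

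- PK set = N − a − c
- PD set = N − b − c
- Union (SAP 5.1.5 as written) = N − c
- Intersection (in both sets) = N − a − b − c

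Neither a nor b appears in the union, so exclusion from one set never changes who is in the primary set. With N = 18 and c = 0, where a and b are assumptions because the documents give no expected number of exclusions:

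| a | b | PK set | PD set | Union | Intersection |
|---|---|---|---|---|---|
| 0 | 0 | 18 | 18 | 18 | 18 |
| 1 | 0 | 17 | 18 | 18 | 17 |
| 1 | 1 | 17 | 17 | 18 | 16 |
| 2 | 2 | 16 | 16 | 18 | 14 |
| 3 | 3 | 15 | 15 | 18 | 12 |

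**Do the dataset rules restore the exclusions?** They act on records, not on participants.

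- PK dataset (SAP 10.5.1): concentrations below the LLOQ are censored and records with missing values or times are ignored. Then: "Records flagged to be ignored will be removed from the dataset".
- PD dataset (SAP 10.5.2): counts below the LLOQ are censored and counts with more than 10% gametocytes are flagged. Then: "Observation records with missing values and records with missing times will be ignored. Records flagged to be ignored will be removed from the dataset". SAP 10.5 also flags parasite data after rescue.

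No rule says that exclusion from the PK or PD set sets a flag. None limits the PD dataset to members of the PD set, or to participants who are also in the PK set.

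**Does model evaluation restore them?** SAP 10.6.1.1 uses the individual PK fits to judge whether the individual estimates are adequate as regressors. It gives no criterion for leaving a participant out. It also concerns only the PK side, so it does not address a participant excluded from the PD set.

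**Head-count.** One participant out of 18 is 1/18 = 5.6%.

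**The case against.** The strongest reply is that a union is natural for a stepwise analysis. The PK dataset holds dosing and concentration records, the PD dataset holds dosing records and parasite counts, and one label covering both steps must include everyone used in either. A participant outside the PD set can properly inform the population PK model. This stands, and it means that route is a fault only at the PD step. It does not rescue the text, because 5.1.5 and Section 10 do not say which set applies to which step. Even if the PK set is meant for the PK step and the PD set for the PD step, a member of the PD set who was excluded from the PK set would still need PK regressors.

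The second reply is that safeguards exist. Flagged records are dropped, the individual PK fits are reviewed, and the PD set's clause on other circumstances could be used against a participant with unusable PK. These reduce the risk. All of them rest on case-by-case judgement, and none follows from set membership.

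Third, a participant with no usable concentrations is unlikely. Dosing is directly observed (Protocol 6.4), and each participant has 18 post-dose inpatient samples and 13 outpatient sampling days (Protocol 8.2.1). That is fair. The more plausible case is a PK-relevant deviation in someone whose concentrations were measured and not flagged.

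Finally, Protocol Section 9 mentions a Modelling Analysis Plan that is not among the documents and might settle this. However, Protocol 9.4.2 says that the full modelling details will be in the SAP.

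**Conclusion.** The point holds as a defect in the definition. As written, only exclusion from both sets removes a participant from the primary set, and no stated rule keeps someone excluded from one set out of the PD step. It has consequences only if at least one participant is excluded from exactly one set and the relevant records are not flagged by other means.

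The size of any effect on Emax, EC50 or MIC cannot be computed from the documents. At the maximum of 18, one participant is 5.6% of the data set by head-count; the share is larger if the study stops with fewer. This is not a measure of bias.

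A reader might infer three stronger things that the documents do not support:

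- **That one such participant is half of a dose group.** The proposed Cohort 1 groups do have n=2, but the primary model pools all doses. The dose-specific PRR48 from log-linear regression is analysed on the PD set (SAP 11.1), which this definition does not touch.
- **That invalid profiles enter the model unchecked.** They do so only where the records are unflagged and the review of individual fits does not lead to their removal.
- **That anyone outside the PD set should be barred from the whole primary analysis.** Such a participant may validly contribute to the PK step.

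**What to change.** Make two linked edits to the SAP.

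1. In 5.1.5, define the PK/PD set as participants who belong to both the PK set and the PD set.
2. In Section 10, replace the single analysis-set line with one set per step:
   - population PK model: PK set;
   - pre-treatment growth model: PD set, since this step needs no concentrations;
   - drug-effect model and the parameters derived from it (MIC, MPC90, PRR48): PK/PD set, meaning participants in both.

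Naming the set per step matters. Intersecting the sets throughout would discard usable concentrations from participants excluded only from PD, and usable growth data from participants excluded only from PK.

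The cost is a few lines of text and no new data. The small downside is that the drug-effect step loses a + b participants compared with the union. With 18 dosed and, by assumption, one excluded from each set alone, the PK and growth steps would each use 17 participants and the drug-effect step 16, against 18 under the present wording.

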6. PROTOCOL DEVIATIONS

Analysis Set: FAS

All protocol deviations will be listed, grouped by participant and dose group

The protocol deviation summary table will capture all deviations as minor deviations and all violations as important deviations. A footnote will be added to the summary table documenting the change.

The protocol deviation summary table will include:

- The total number of minor protocol deviations
- The total number of important protocol deviations
- The number of Participants who reported at least one minor protocol deviation
- The number of Participants who reported at least one important protocol deviations

7. PARTICIPANT DISPOSITION

Analysis Set: FAS

Disposition

A listing of participant disposition will present:

- Date of informed consent
- Date of inoculation
- Date of IMP administration
- Date of rescue medication administration including Primacin
- Did the participant complete the study?
- Date of completion / early withdrawal
- Primary reason for early withdrawal (including instances where early termination was related to COVID-19)

Detailed early withdrawal information will also be listed in a separate listing.

If there are any deaths reported, a separate death listing will be prepared.

The number and percentage of Participants entering and discontinuing the study will be summarised by dose group and overall along with the reason for discontinuation. The participant disposition summary table will include:

- Number of participants signed informed consent
- Number of participants who received IMP
- Number of participants who completed the full study
- Number of participants withdrawn from the study early
- Reason for early withdrawal

8. DEMOGRAPHIC AND BASELINE INFORMATION

Analysis Set: FAS

8.1 Demographics

Demographic data will be listed for all enrolled participants and summarised by dose group and overall. Data includes:

Age
Sex
Women of Child-bearing potential
Post-menopausal
Race
Ethnicity
Weight (kg)
Height (m)
BMI (kg/m²)

8.2 Medical History

All medical history data will be listed, grouped by participant.

Medical history will be coded using the Medical Dictionary for Regulatory Activities (MedDRA version 24.1) and summarised by system organ class (SOC) and preferred term (PT).

8.3 Prior Medications

Prior medications are defined as any medication that is started before first inoculation with the malaria challenge agent, regardless of when it ended. If a medication has a missing or partial

missing start/end date or time and it cannot be determined whether it was taken before IMP or concomitantly, it will be considered as prior and concomitant. Medications will be coded using WHODrug Dictionary September 2021 release.

Prior medications will be summarised by Anatomical Therapeutic Class (ATC) and preferred name (PN) and will also be listed. The summary tables will show the number and percentage of participants taking each medication by ATC and PN.

8.4 Drug Screen

Drug screen data will be listed for all participants.

8.5 Alcohol Screen

Alcohol screening data will be listed for all participants.

8.6 SARS-CoV-2 Screening

Any positive SARS-CoV2 screening results will be listed.

8.7 Follicle Stimulating Hormone (FSH)

FSH results will be listed for Post-menopausal women only.

8.8 Beck Depression Inventory

Beck Depression Inventory (BDI-II) data will be listed for all participants, including answers to the individual questions as well as the total scores, which are auto-calculated within the CRF.

9. TREATMENT EXPOSURE

Analysis Set: FAS Set

Participant exposure to the protocol-specified treatments (IMP, malaria challenge agent and rescue medications Riamet, Malarone, IV Artesunate and Primacain) will be listed and summarised by dose of IMP and overall.

10. PRIMARY ENDPOINT ANALYSIS (PK/PD ANALYSIS)

Analysis Set: PK/PD Analysis Set

10.1 Overview of methodology for PK/ PD Modelling

A population PKPD model will be derived from the concentrations and parasitemia observed in the challenge participants. It is achieved by sequentially developing a population PK model to describe the observed individual PK profiles and a population PD model for quantifying the relationship of blood concentrations and the parasite clearance.

Then, the PD model is combined with a PK model in malaria patients to predict the parasitemia profiles this population, assuming the PKPD relationship will be the same in patients as in the challenge participants.

10.2 Sources of Data

Data from study MMV_Pyronaridine_21_01 will contain information on the individual Pyronaridine tetraphosphate doses, Pyronaridine* PK concentrations, the triplicated parasitemia levels, gametocyte data and typical covariates such as age, height, weight, sex and race

10.3 Pharmacokinetics

Blood for Pyronaridine concentrations will be collected pre-Pyronaridine tetraphosphate administration on Day 8, then at the following hours post-Pyronaridine tetraphosphate administration while confined in the clinical unit: 1, 2, 3, 4, 6, 8, 12, 16, 20, 24, 30, 36, 42, 48, 60, 72, 84 and 96 hours. As outpatients, participants will have blood collected on the following days: 13, 15, 17, 20, 22, 24, 27, 29, 32, 39, 44, 47 and 50.

10.4 Pharmacodynamics

10.4.1 Malaria 18S qPCR

Blood will be collected to quantify total malaria parasitemia by quantitative polymerase chain reaction targeting the gene encoding *P. falciparum* 18S rRNA (malaria 18S qPCR; reported as parasites/500uL packed RBCs). Malaria 18S qPCR data will be used to calculate the total parasite counts. Blood for malaria 18S qPCR will be collected on Day 0 prior to inoculation with the malaria challenge agent, then once daily on Days 4, 5, 6 and 7. On Day 8, blood will be collected pre-Pyronaridine tetraphosphate administration, then at the following hours post-Pyronaridine tetraphosphate administration while confined in the clinical unit: 4, 8, 12, 16, 20, 24, 30, 36, 42, 48, 60, 72, 84 and 96 hours. As outpatients, participants will have blood collected at least three times per week until antimalarial rescue treatment.

10.4.2 Parasite lifecycle stage qRT-PCR

Additional blood samples may be collected to evaluate the presence of sexual parasite stages (gametocytes) and other parasite lifecycle stages using quantitative reverse-transcriptase polymerase chain reaction (qRT-PCR). The qRT-PCR assays will be done for the following targets: the female gametocyte-specific transcript pfs25, the male gametocyte-specific transcript PfMGET, and the ring-stage transcript pfSBP-1.

10.5 Data Assembly

First a master dataset will be assembled formatted according to the MMV dataset standard. (cf., "MS_IQdataset_V4_20210219.docx"). Blood concentration will be in ug/mL, total parasite levels in counts/mL, and doses in mg. Gametocyte data is in copies/uL.

Parasite data after the first administration of rescue medication is flagged by setting the IGNORE column to "Rescued". The time in hours is relative to the (first) Pyronaridine tetraphosphate administration time.

A general analysis dataset is derived from the master dataset. Gametocyte data will be converted to parasite counts following the instructions in "Analyzing RNA data by [name] Nov2017.docx". Total counts of parasites were flagged to be ignored (by setting the column IGNORE to "gametocytes") if counts of gametocytes exceeded 10% of total counts.

The viable parasites counts will be derived by multiplication of the viable fraction values with the mean parasite count at treatment administration.

A general analysis dataset is derived from the master dataset. The general analysis dataset will contain the following observations: Pyronaridine blood concentrations, total counts of parasites, as well as counts of gametocytes and viable parasite counts. In addition, dosing records for *P. falciparum* inoculation, Pyronaridine tetraphosphate administration and rescue medication administration will be defined. It is advised to define additional columns DOSELEVEL and DOSEMULT to indicate the dose amount and number of doses a participant received as covariate columns.

NLME datasets for the PK and PD modeling will be derived from the general dataset.

